3.2 Exclusion Criteria

Clinicians. There are no exclusion criteria for clinicians.

Patients. Visits will be excluded from the primary analysis when they have active cancer. Cancer exclusions (ICD-10 codes) are listed in Appendix A.

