3.3 Study Enrollment Procedures

We will seek a waiver of consent for clinician and patient participation. All clinicians treating patients who meet the inclusion criteria in participating practices will be contacted by email to inform them that their patients will be receiving the following assessments: COMM or COMM+PainTracker, depending on clinician study arm assignment.

The COMM is already being delivered as part of standard clinical care. Our study proposes to randomize half of the patients to also receive the PainTracker, which poses no additional risk.

We are requesting a waiver of consent under the Common Rule. The Common Rule (§46.116) specifies that informed consent can be waived when: “(1) The research involves no more than minimal risk to the subjects; (2) The research could not practicably be carried out without the requested waiver or alteration; (3) If the research involves using identifiable private information, the research could not be practicably carried out without the identifiable information; (4) The waiver or alteration will not adversely affect the rights and welfare of the subjects; [and] (5) Whenever appropriate, the subjects will be provided with additional pertinent information after participation.”

Withdrawal of subjects: Patients receive COMM as part of their standard of care at Northwestern Medicine. Patients will not be required to respond to the additional PainTracker surveys, and will continue to receive the same standard of care. After the 9 month intervention, PainTracker surveys will no longer be delivered to patients.

STUDY INTERVENTIONS

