3.5 Handling of Study Interventions

The following study arms will be compared:

Condition 1 (COMM) - On a monthly basis, as part of standard clinical care, patients will receive the Current Opioid Misuse Measure, a 17-item self-report screener to identify and monitor the risk of aberrant opioid-related behavior in chronic pain patients on opioid therapy. The COMM asks patients to report their behaviors over the past 30 days using a five-point Likert-type rating scale. Multiple studies have shown that the COMM can accurately identify patients who are engaging in aberrant opioid-related behavior (defined as medication misuse, abuse, addiction, diversion, and opioid-seeking behaviors) with approximately 80% accuracy. Much of its classification accuracy is because many of the items, while predictive of opioid misuse, do not appear to patients to be asking about opioid misuse.

Condition 2 (COMM+PainTracker) - On a monthly basis, patients will receive both the Current Opioid Misuse Measure (described above) and PainTracker. The latter tracks multiple outcomes relevant to the treatment of chronic pain: pain severity, general activity interference, enjoyment of life interference, sleep (initiating and maintaining), depression, and anxiety. New and returning patients are asked to complete the PainTracker assessment at least one week prior to their appointment.

COMM and PainTracker surveys will be delivered through the patient portal and survey responses will be recorded in the patient electronic health record, and will be visible to the patient's doctor at the time of their next visit. USC will not receive patient survey data, only completion rates.

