4.2.2 Enrollment, Baseline, and/or Randomization

Enrollment

This study involves a randomized trial with 286 clinicians to inform the best approaches to patient assessments for opioid at clinical visits. Long-term opioid recipients complete the Current Opioid Misuse Measure as standard clinical practice. PainTracker will appear as part of these required assessments randomly for half the patients of clinicians randomized to the intervention (COMM+PainTracker). If a waiver is granted, enrollment date (RCT implementation date) will be recorded for each clinic.

Assessments

Baseline: At baseline, we will assess clinician baseline prescribing monthly morphine milligram equivalents (MMEs), ICD-10 codes, and ordering data.

Enrollment and Randomization (Day 1). Demographics, inclusion/exclusion criteria, ICD-10 codes, and ordering data.

Intervention start (Month 1). ICD-10 codes, and ordering data, Pain Tracker/COMM completion rates, Referral rates to non-opioid care, adverse events

Continuously measured or monitored. ICD-10 codes, and ordering data, Pain Tracker/COMM completion rates, Clinician

monthly MMEs, Referral rates to non-opioid care, adverse events

Intervention end (Month 9): ICD-10 codes, and ordering data, Pain Tracker/COMM completion rates, Referral rates to non-opioid care, adverse events

Follow-up (Month 10-12): ICD-10 codes, ordering data, Clinician MMEs, Referral rates to non-opioid care.

Randomization

We will use cluster randomization at the physician level to avoid contamination that might occur if individual providers are randomized to multiple interventions. We will carry out block randomization of physicians with respect to historical referral rate (high vs. low) by using a random permutation of physician lists in the statistical computing language R. Patients of clinicians in the first half of the permuted list will receive the PainTracker survey intervention in addition to COMM. The second half will receive the control condition (COMM standard clinical practice). The same intervention (PainTracker survey) will be implemented throughout the 9 month study period. No intervention will occur during the 3 month follow-up period; it will be for outcomes assessment only.

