5.1 Specification of Safety Parameters

Data elements from qualifying visits for providers enrolled in the study will be collected from the electronic health record. Aggregate counts of total visits across sites for which the intervention was implemented, for high dose opioid patients, if abrupt changes to dose (> 20% morphine equivalent daily dose) were made. Such cases will be examined closely to determine if unsafe drops in opioids occurred.

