7.3 Outcomes

7.3.1 Primary outcome

The primary outcome is the referral rate to non-opioid related care. This includes: mental health, physical therapy and sleep medicine referrals. We will also measure the rate of new starts on antidepressants.

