7.3.2 Secondary outcomes

Secondary outcomes include: 1) clinician aggregate monthly milligram (mg) morphine equivalent (ME) and 2) benzodiazepine prescribing. We will estimate the daily milligram morphine equivalent for each clinician by summing the total number of daily morphine equivalents written within a monthly observation period divided by the number of 30 days. For example, suppose a clinician has three qualifying visits over three days in one month and prescribed as follows: Patient #1 is prescribed 200mg ME/day x 30 days, Patient #2 has tapered from 200 mg ME/day to now 100mg ME/day x 30 days and Patient # 3 is on a tapering plan from 60 to 30 mg ME/day and receives 50 mg ME/day x 15 days. The clinician's outcome for that month then equals:

$$\begin{aligned} & [(200 \text{ mg/day} \times 30 \text{ days}) + 100 \text{ mg/day} \times 30 \text{ days}) + (50 \text{ mg/day} \times 15 \text{ days})] \times [1 \text{ Month}/30 \text{ days}] \\ & = (300 \text{ mg} \times 1 + 100 \text{ mg} \times 1 + 50 \text{ mg} \times (\frac{1}{2})) = 425 \text{ mg MED}/[\text{Month}]. \end{aligned}$$

Oral buprenorphine will be excluded from the calculations as it relates to opioid use disorder treatment. Morphine equivalent dose will be computed by standard means described elsewhere.²⁸ Benzodiazepines will be handled similarly to monthly milligram morphine equivalents but with valium morphine equivalents. Qualifying pain visits will be captured by including all ICD-10 pain diagnostic codes and excluding active cancer diagnoses.

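### The secondary prescribing outcomes count only visits selected by pain codes recorded after randomisation, so a difference in coding between arms can create or hide a difference in prescribing

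*Combined protocol and SAP*

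**What the plan says.** Section 3.1 fixes the patient cohort in advance: people aged 65 or older in the chronic opioid registry with a primary care encounter in a 12-month window ending 8/08/2023. No pain code is required for entry.

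Section 7.3.2 then restricts what is counted for the secondary outcomes: "Qualifying pain visits will be captured by including all ICD-10 pain diagnostic codes and excluding active cancer diagnoses". The morphine-equivalent outcome is a monthly clinician total, illustrated with three qualifying visits. Benzodiazepines are to be treated in a similar way.

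The primary outcome is defined without that restriction: "The primary outcome is the referral rate to non-opioid related care" (section 7.3.1). The only filter written for it is in section 3.2: "Visits will be excluded from the primary analysis when they have active cancer".

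On timing and knowledge of arm:

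- Section 3.3, on what clinicians are told: "contacted by email to inform them that their patients will be receiving the following assessments: COMM or COMM+PainTracker, depending on clinician study arm assignment".
- Section 3.5: survey answers "will be visible to the patient's doctor at the time of their next visit".
- Section 4.2.2 lists diagnosis codes among the items collected during the intervention: "Continuously measured or monitored. ICD-10 codes, and ordering data, Pain Tracker/COMM completion rates". They are also collected in months 10 to 12.

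The only related quality check, in section 8.3.3, is a report that visits were not cancer exclusions.

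**The concern.** Randomisation protects a comparison of everything the clinicians prescribe to a cohort fixed beforehand. It does not protect a comparison of prescribing at visits chosen by a variable recorded later, if treatment can affect that variable.

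Treatment could plausibly affect it here. Sections 2.2 and 3 rest on the idea that what is asked and talked about at the visit shapes the care given, and section 2.2 describes PainTracker as moving the conversation beyond pain intensity. If some visits are then coded for mood, trauma or sleep and carry no pain code, their opioid orders leave the outcome. The pain-location grid in Appendix B could act the other way and prompt pain codes that would not otherwise be recorded.

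The secondary hypothesis in section 7.4 is that morphine-equivalent dose falls with PainTracker in patients on high doses. Fewer pain codes in the PainTracker arm would imitate that result, and more would mask it. Since the direction is unknown, the filter cannot be defended as conservative.

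**Working it through.** **1. The plan's own example.** Section 7.3.2 gives three prescriptions: 200 mg/day for 30 days, 100 mg/day for 30 days and 50 mg/day for 15 days.

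(200×30 + 100×30 + 50×15) / 30 = (6000 + 3000 + 750) / 30 = 325.

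The plan prints 425, because its second line has 300 where the inputs give 200. That slip is a separate matter and needs reconciling. I use 325; the percentages in step 3 do not depend on it.

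**2. One missing code, same prescribing.**

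| Visit without a pain code | Clinician total |
|---|---|
| none | 325 |
| Patient 3 | (6000 + 3000)/30 = 300 |
| Patient 2 | (6000 + 750)/30 = 225 |
| Patient 1 | (3000 + 750)/30 = 125 |

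**3. Expected size over many visits.** Let c be the share of the prescribed amount written at visits with a pain code. If coding is unrelated to dose, the counted total is the true total × c. With identical prescribing, the ratio between arms is therefore c₁/c₀. The documents give no value for c, so these are assumptions:

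- 80% vs 85%: 325×0.80 = 260 and 325×0.85 = 276.25; 0.85/0.80 = 1.0625, a difference of 6.25%.
- 80% vs 90%: 260 and 292.5; 0.90/0.80 = 1.125, a difference of 12.5%.
- Lower share 70% to 90%, gap 2 to 10 points: from 0.92/0.90 − 1 = 2.2% to 0.80/0.70 − 1 = 14.3%.

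If PainTracker is the arm with the lower share, the same gaps appear as falls: 0.80/0.85 − 1 = −5.9% and 0.80/0.90 − 1 = −11.1%.

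**4. Does the planned model remove this?** Model [1] in section 7.4 has group-specific slopes before and after the start date t*, and no jump at t*. Data from before t* cannot correct a coding change that begins at t*. If capture in one arm drifts steadily from 80% to 90% over the nine months, and stays at 80% in the other, the drift alone gives a difference in slope change (β₆) of 325×0.10/9 = 3.6 per month. An abrupt change is not represented in the model. How it spreads over the group terms depends on the lengths of the pre- and post-periods, and the length of the baseline series is not stated.

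**5. Planned safeguards.** I found no analysis without the filter, and no comparison by arm of qualifying-visit counts or pain-code rates.

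**The case against.** Several counter-arguments have force.

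- **Adding a code removes nothing.** Section 7.3.2 admits a visit with any pain code. A depression or insomnia code added to a pain code leaves the visit in; the pain code itself must be absent. This stands, and makes large losses less likely. It does not exclude smaller ones, or gains from extra pain codes.
- **Who assigns the codes is not stated.** Section 8.1 mentions only electronic medical and billing records. That the treating clinician's choices drive the codes is a reasonable inference and no more.
- **The model may use a mean.** Section 7.4 speaks of a monthly mean daily dose. If this is a mean per visit, loss unrelated to dose would not scale it. Selective loss still would: in the example the mean is 325/3 = 108.3 with all visits and 300/2 = 150 without Patient 3. Section 7.3.2 in any case defines a clinician total.
- **A level ratio is not what model [1] estimates.** Correct. The percentages describe the outcome and are not a predicted bias in a coefficient.
- **For benzodiazepines, the similar handling may mean only the milligram calculation.** The text leaves this open.

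A reader might also infer more than the documents support:

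- *All outcomes are filtered on pain codes.* The filter is written only under secondary outcomes. The primary analysis has only the cancer exclusion.
- *PainTracker alters cancer coding.* No route for this is described. A patient who moves in and out by visit is not in itself a difference between arms.
- *All safety counts inherit the problem.* Section 5.1 says "Data elements from qualifying visits for providers enrolled in the study will be collected from the electronic health record" but does not define the term. Emergency visits and hospitalisations in section 5 and adverse events in section 5.3 are not tied to pain-coded visits.

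**Conclusion.** The concern holds for the secondary outcomes: for clinician monthly morphine equivalents by the plain text, and for benzodiazepines if their similar handling includes the visit filter. The visits that count are chosen by codes recorded after randomisation, by or for clinicians who know the assessments and see the answers. The outcome is a total, so the choice of visits enters it directly. The plan has no check that would reveal a coding difference.

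The size is unknown. About 6% for a 5-point gap and 12.5% for a 10-point gap, from an 80% base, are illustrations that rest on assumed capture shares, identical prescribing and coding unrelated to dose. The direction could be either way. That such a gap will occur is plausible from the trial's own rationale but is not shown.

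The documents do not support extending this to the primary referral outcome. For that outcome a clarifying sentence is enough. The change is worth making because it removes the dependence at little cost.

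**What to change.** In section 7.3.2:

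1. Define the main secondary analysis on the section 3.1 registry patients, fixed before randomisation. Count all opioid and benzodiazepine orders written for them by the randomised clinicians, whatever diagnosis is coded at the visit. Keep the existing buprenorphine rule.
2. For this analysis, base the cancer exclusion on Appendix A codes in the baseline diagnosis data already scheduled in section 4.1.
3. Keep the pain-code filter, and the visit-level cancer exclusion using codes recorded after randomisation, as sensitivity analyses.
4. Report the number of qualifying visits and the share of visits with a pain code, by arm and month, before and after the start date.
5. State that the pain-code filter does not apply to the primary referral outcome, and say in section 5.1 what a qualifying visit means there.
6. Say whether the benzodiazepine outcome follows the same visit rule, and whether section 7.4 models the clinician total or a mean.

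The cost is a change of wording and a wider query; ordering data and diagnosis codes are already collected. The change should be made before the end-of-study extract described in section 8.2. The downside is that some orders unrelated to pain, and some patients with cancer first diagnosed after randomisation, stay in the main analysis and add noise. The sensitivity analyses show how much that matters.

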7.4 Data Analyses

For inferential analysis, our *primary hypothesis* is that the proportion of non-opioid referrals will be greater among physicians treating patients who receive PainTracker. We evaluate this with a zero-inflated Poisson model to estimate the number of referrals to non-opioid related care which is then divided by the average number of referrals for each group to estimate the proportion. Our *secondary hypothesis* is that milligram morphine equivalent dose will decrease for persons on high doses of opioid therapy receiving PainTracker. We assume a linear mixed-effects hierarchical knotted spline regression model which offers a flexible way to accommodate non-linear trends before and after the introduction of the intervention.²⁰ This model places a knot at the intervention start date allowing slopes before and during treatment to vary for intervention and control. For our two-group study evaluating this outcome, monthly mean milligram morphine daily dose prescribed for intervention and control, we will place a knot at t^* , the start of the intervention, and evaluate for each comparison between groups:

$$Y = \beta_1 + \beta_2 \text{Time} + \beta_3(\text{Time} - t^*)_+ + \beta_4 \text{Group} + \beta_5 \text{Time} \times \text{Group} + \beta_6(\text{Time} - t^*)_+ \times \text{Group} + \eta + \text{error} \quad [1]$$

where $(z)_+$ is a truncated line function that equals z when z is positive and is equal to zero otherwise, and η is the clinic random effect.

8. **DATA COLLECTION AND QUALITY ASSURANCE**

8.1 **Data Collection Forms**

Data will be collected from electronic medical and billing records and completion rates of PainTracker and COMM surveys.

8.2 **Data Management**

Each of the participating sites will create an extract from their Electronic Medical or Billing Records of the Data Elements. These records will be transferred to the coordinating center as a one time HIPAA compliant limited data set at the end of the study. The CC has created programs and quality control queries for transforming all of the data into a standard model (Observational Medical Outcomes Partnership Common Data Model, version 5.3.1).

The electronic data system, Epic, will have native data capture formats.

Data will be recorded with SSL-protected websites to a data warehouse, and transferred over a secure network protocol. Data will be kept in encrypted files on a secure research computing cloud at USC Schaeffer Center facilities. Study investigators will have access to a list of study ID codes that will be traceable back to actual subject contact identifiers for clinicians. These codes will be kept in locked offices at USC Schaeffer Center facilities. USC and Northwestern University have a fully executed Data Use Agreement in place.

8.3 **Quality Assurance**

8.3.1 *Training*

Staff will be trained on the permissible values present in Electronic Records, frequency of update, and expected volumes of data.

8.3.2 *Quality Control Committee*

The quality control committee will consist of practicing clinicians from Northwestern Medicine.

8.3.3 *Metrics*

Quality control metrics will be based on reports verifying visits were not for cancer exclusions. All drugs prescribed at these visits will be categorized as “opioid” or “non-opioid”.

8.3.4 *Protocol Deviations*

Our task tracking systems, JIRA and Monday.com will be used to track and document issues. Each issue will include both an assignee and a reviewer.

8.3.5 *Monitoring*

In addition to data quality reviews, we will also review the integrity of the interventions. On an approximately quarterly basis, staff will verify functionality of decision support tools. Additionally, practicing clinicians on our study team will have the ability to monitor electronic medical record interventions in their own health systems.

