7. STATISTICAL CONSIDERATIONS

7.1 Sample Size and Randomization

Sample Size: We conduct power on the discrete outcome of the referral. The rate of referrals for mental health and pain treatment is low at Northwestern, but if combined with sleep and physical therapy will be at least 5%. There are 300 clinicians who treat patients at the Northwestern outpatient clinics. There are also 5,159 persons over 65 years of age on long-term opioid therapy within patient registries at Northwestern University's health system with at least one primary care encounter in the past 12 months. Assuming 150 clinicians per condition, each treating 17 patients (i.e., 2,500 patients per condition), $\alpha = 0.05$ for a two-sided

test, an intraclass correlation coefficient of 0.06, and an 80% chance of detecting an effect, requires a 3% difference between groups when the baseline referral rate is 5% and 4% difference between groups when the baseline referral rate is 10% (see **Figure 2**).

Figure 2

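### The primary zero-inflated Poisson model states no clinician clustering, unit of analysis or offset, so as written it does not protect the two-sided 5% level

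*Combined protocol and SAP*

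**What the plan says.** On randomisation, section 4.2.2 states: "We will use cluster randomization at the physician level to avoid contamination". Patients follow their clinician's assignment: "Patients of clinicians in the first half of the permuted list will receive the PainTracker survey intervention in addition to COMM". Clinicians are blocked by historical referral rate, high or low.

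The power calculation in section 7.1 uses "an intraclass correlation coefficient of 0.06", 150 clinicians per arm with 17 patients each (2,500 patients per arm), two-sided alpha 0.05 and 80% power. Section 3 gives different counts: 286 clinicians and 1,451 patients.

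The primary analysis in section 7.4 is: "We evaluate this with a zero-inflated Poisson model", applied to the count of non-opioid referrals. The estimate is then divided by an average number of referrals in each group. There is no equation for this model and no statement of what one record is (visit, patient, clinician or clinician-month). No offset, clinician effect or variance method is given. The secondary spline model for morphine equivalents does have a random effect, but at another level: "η is the clinic random effect".

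**The concern.** Patients of one clinician share that clinician's referral habits. When clinicians are randomised, this shared variation enters the arm comparison in full. A model that treats records as independent within arm gives a standard error that is too small. A model of clinician totals without an offset also turns differences in panel size into extra variation, which a Poisson count part does not carry. The design counts this correlation when it sets the sample size, but the stated primary analysis does not. At stake is the trial's primary test: a nominally significant result could partly reflect which clinicians fell in which arm.

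**Working it through.** **1. Does section 7.1 allow for clinician clustering?** Inputs from 7.1: n = 2,500 per arm, m = 17, ICC = 0.06, two-sided alpha 0.05, power 80%.

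- Design effect: DE = 1 + (m − 1) × ICC = 1 + 16 × 0.06 = 1.96.
- Effective n per arm: 2,500 / 1.96 = 1,276.
- The detectable difference d solves d = 1.960 × √[2p̄(1 − p̄)/n] + 0.842 × √[(p₁(1 − p₁) + p₂(1 − p₂))/n], where p₂ = p₁ + d, p̄ is the mean of p₁ and p₂, and n = 1,276.
- Result: 2.70 points at a 5% baseline and 3.58 points at 10%. These round to the stated 3 and 4 points.
- Without the design effect (n = 2,500) the results would be 1.87 and 2.50 points. The ICC was therefore used.

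**2. What if the analysis leaves clinician out?** A nominal 5% test then has true type I error 2 × [1 − Φ(1.96/√DE)].

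- Section 3 enrolment: m = 1,451/286 = 5.07, DE = 1 + 4.07 × 0.06 = 1.244, √DE = 1.116. Type I error is 7.9% and interval coverage 92.1%.
- Section 7.1 enrolment: m = 17, DE = 1.96, √DE = 1.40. Type I error is 16.2% and coverage 83.8%.
- If the ICC is anywhere from 0.01 to 0.10 (my range), the error is 5.5-9.9% at 5.07 patients per clinician and 6.9-22.4% at 17.

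This formula assumes equal panels and a simple comparison of proportions. It is not the zero-inflated Poisson model itself.

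**3. Null simulations of the zero-inflated Poisson model.** ICC 0.06, baseline referral rate 5% and 10%, model-based standard errors. There were 1,000 runs per setting with equal panels and 2,000 with unequal panels (Monte Carlo standard error about 0.5 to 1 point).

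Assumptions not in the documents: beta-binomial variation between clinicians, constant zero inflation, the arm effect in the count part only, panel-size CV 0.8 where panels are unequal, and 1 + Poisson(0.5) referrals per referred patient for patient rows. Blocking was not simulated.

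| Records in the model | About 5 per clinician (286 clinicians) | 17 per clinician (300 clinicians) |
|---|---|---|
| Patient rows, equal panels | 6.4-7.2% | 9.7-9.9% |
| Clinician totals, equal panels | 4.6-5.5% | 8.5-9.9% |
| Clinician totals, unequal panels, offset | 5.5-5.9% | 15.2-16.2% |
| Clinician totals, unequal panels, no offset | 7.1-8.9% | 19.6-24.4% |

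With clinician-robust standard errors, the error over all these settings was 4.4-6.7%.

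**4. Effect of blocking (illustration).** Assume normally distributed referral propensities and a median split on historical rate, which correlates r with true propensity. The split then removes (2/π)r² of the between-clinician variance, so DE = (1 − ICC) + m × ICC × [1 − (2/π)r²].

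- For r = 0.5, 0.7 and 1.0, the 7.9% becomes 7.3%, 6.8% and 5.6%.
- For the same r, the 16.2% becomes 14.4%, 12.6% and 8.7%.

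**The case against.** The strongest reply is that 7.4 is brief rather than wrong. One sentence describes the model, and silence about clinicians is not a decision to ignore them. The hypothesis is worded in terms of physicians, so one record per clinician is a fair reading. With a panel-size offset and the section 3 enrolment, that reading is close to nominal (5.5-5.9%, or 4.6-5.5% with equal panels). This part stands. A reader might infer that the p-value is too optimistic whatever the unit of analysis. The documents do not support that, because they leave the unit open. The reply does not rescue the plan, however: neither the unit nor an offset is stated, and at 17 patients per clinician the same reading still gives 15.2-16.2%, since zero inflation absorbs only part of the between-clinician variation.

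Blocking by historical referral rate also counts against the larger figures. It limits imbalance in high-referring clinicians between arms. In the illustration it reduces the inflation without removing it.

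A reader might also infer inflation of 17-23% at about 5 patients per clinician. That needs three referral opportunities per patient, a number found nowhere in the documents. Sparser assumed counts gave 6.4-7.2%.

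Finally, the Précis and section 3.3 speak loosely of half the patients, which might suggest that patients were randomised individually. I rely on the explicit Randomization paragraph in 4.2.2 and on the use of a clinician-level ICC in 7.1.

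**Conclusion.** The omission is real. Clinicians are the randomised clusters and the sample size accounts for that, but the primary analysis as written does not, and no other section fills the gap. The clinic effect in the secondary model does not help, because it sits in a different model and at a different level.

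The size is conditional. At the section 3 enrolment the true type I error is 7.9% by formula and about 5-9% in simulation. If the 17 patients per clinician of section 7.1 apply, it is 16.2% by formula and about 9-24% in simulation. The result rests on ICC 0.06, on the assumed panel-size spread where panels are unequal, on the unstated unit of analysis, and on which enrolment count holds. Blocking would bring the figures down somewhat. The supportable statement is that the 5% level is not protected, not that it is breached by a known amount. Because this is the primary test and the repair is only text, it should be corrected before analysis.

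**What to change.** In section 7.4:

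- State the unit of analysis for the primary model. If clinician totals are modelled, add an offset for the log number of eligible patients.
- Add a clinician random intercept, or use clinician-level cluster-robust variance (GEE or sandwich).
- Include the blocking factor, historical referral rate high or low, as a covariate.

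Patient records are not required; either unit can work if clustering is handled. A small-sample correction is not shown to be needed with about 143 clinicians per arm (286/2), given the 4.4-6.7% found with robust errors.

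The cost is a few lines of text and a somewhat wider interval: by formula, the standard error is multiplied by about 1.12 at 5.07 patients per clinician and 1.40 at 17. The section 7.1 calculation already includes the allowance for clinician clustering. No change to recruitment or data collection follows.

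### The primary estimate in section 7.4 has no valid denominator, and on neither reading of its wording does it give the referral rate that the plan defines and powers

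*Combined protocol and SAP*

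**What the plan says.** All references are to the combined protocol and SAP.

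- **7.4 Data Analyses.** The primary hypothesis is that "the proportion of non-opioid referrals will be greater among physicians treating patients who receive PainTracker". It is to be evaluated with a zero-inflated Poisson (ZIP) model, used "to estimate the number of referrals to non-opioid related care which is then divided by the average number of referrals for each group"; the quotient is then taken as the proportion. Nothing more is said about the primary analysis. No offset, unit of count, group contrast or treatment of clustering is given for it. The mixed model with a clinic random effect later in 7.4 is for the morphine-equivalent outcome.
- **7.3.1 Primary outcome.** "The primary outcome is the referral rate to non-opioid related care", with the qualifying types of referral listed. No denominator is given.
- **7.1 Sample Size and Randomization.** "We conduct power on the discrete outcome of the referral". The inputs are baseline rates of 5% or 10%, 150 clinicians per arm with 17 patients each (about 2,500 patients per arm), two-sided alpha 0.05, and "an intraclass correlation coefficient of 0.06, and an 80% chance of detecting an effect". The stated detectable differences are 3 and 4 percentage points.
- **3.2 and 4.1.** The cancer exclusion from the primary analysis is worded in terms of visits, and the schedule lists referral rates among the visit-level assessments.
- **4.2.2.** Physicians are the unit of randomisation.

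**The concern.** A proportion or rate needs a denominator of units that could have had the event: patients, visits or person-time. Section 7.4 divides referrals by referrals. The numerator is labelled as non-opioid referrals; the denominator is labelled only as referrals, averaged within each group over an unstated unit. Depending on how an analyst fills those gaps, the quotient is either fixed regardless of treatment or a different quantity from the one defined in 7.3.1 and powered in 7.1. Since this is the only description of the primary analysis, the choice of estimate and test would be left until after the data have been seen.

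**Working it through.** **1. The plan's own figure.** Section 7.1 works on a proportion with patients as the units.

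- Design effect = 1 + (17 − 1) × 0.06 = 1.96.
- Effective patients per arm = 2,500 / 1.96 = 1,276.
- With the usual two-proportion normal approximation (two-sided 0.05, 80% power), the smallest detectable difference is 2.7 points from a 5% baseline and 3.6 points from 10%.
- Rounded up, these are the stated 3 and 4 points. Power at exactly 3 and 4 points is about 87% and 88%.

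The power statement therefore reproduces, and it refers to a per-patient proportion.

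**2. Same referrals in both terms.** Take one arm with *n* clinicians, *n₁* of them with at least one referral, and *S* referrals in all. A ZIP with its own zero-inflation probability π and Poisson mean λ in that arm has maximum-likelihood equations

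- (1 − π)(1 − e^−λ) = n₁/n, and
- λ/(1 − e^−λ) = S/n₁.

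Multiplying them gives (1 − π)λ = S/n: the fitted mean equals the arm's observed mean. So

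- fitted mean / group mean = 1;
- modelled total / group mean = n × (S/n) / (S/n) = n, the number of clinicians.

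A simulated check used 286 / 2 = 143 clinicians per arm, 1,451 / 286 = 5.07 patients each, and true rates of 5% and 8% referrals per patient. It also assumed 40% excess zeros and 0.3 other referrals per patient; neither figure is in the documents. One data set gave:

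| Quantity | Control | PainTracker |
|---|---|---|
| Fitted ZIP mean per clinician | 0.2308 | 0.3986 |
| Divided by the arm's mean non-opioid referrals | 1.000000 | 1.000000 |
| Modelled total divided by that mean | 143 | 143 |
| Divided by patients per clinician | 0.0455 | 0.0786 |
| Divided by the arm's mean of all referrals | 0.1398 | 0.2218 |

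The second and third rows stayed the same at true rate ratios of 1.0, 2.0 and 3.0. Only the last two rows carry treatment information.

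**3. All referrals in the denominator.** With non-opioid referrals at rate *r* per patient and other referrals at rate *o*, the quotient of means is r / (r + o). The documents do not give *o*, so a range is assumed.

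| o per patient | r = 0.05 | r = 0.08 |
|---|---|---|
| 0.1 | 0.05/0.15 = 33% | 0.08/0.18 = 44% |
| 0.3 | 0.05/0.35 = 14% | 0.08/0.38 = 21% |
| 1.0 | 0.05/1.05 = 4.8% | 0.08/1.08 = 7.4% |

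The share moves with the effect, but its level and contrast depend on *o*, which is counted after randomisation. If PainTracker also raised other referrals 1.6-fold, from 0.3 to 0.48, the intervention share would be 0.08 / (0.08 + 0.48) = 14%. That equals control, although the per-patient rate rose from 5% to 8%.

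**4. The test.** A ZIP with group in both parts has two group coefficients, one for excess zeros and one for the count. The plan does not say which is tested, or whether a marginal contrast combining them is meant.

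**5. Clustering in any replacement.** At ICC 0.06 the design effect runs from 1 + (5.07 − 1) × 0.06 = 1.24 (panel size from section 3) to 1.96 (panel size from 7.1). A test that ignored it would use 1.96/√1.24 = 1.76 or 1.96/√1.96 = 1.40 as its effective critical value, so a nominal 5% test would run at about 8% to 16%.

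**The case against.** The strongest reply is that this is a drafting slip in a conversion step. The hypothesis is evaluated with the ZIP model, and a group effect there could be tested whatever the later division yields. The hypothesis speaks of a proportion of non-opioid referrals, which supports reading the denominator as all referrals; that quotient is not fixed. The visit-based wording in 3.2 and 4.1 also suggests that a visit denominator may have been in mind.

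Much of this stands. A reader might infer that the primary analysis must report 1.0 in both arms whatever PainTracker does, and so can never show a difference. The documents do not support that. Exactly 1.0 requires the same referrals in both terms, a mean as numerator, group in both ZIP parts and no other covariates. Section 7.4 fixes none of these, and a modelled total gives the number of clinicians instead.

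What does not stand is that the gap is harmless. The all-referrals reading gives an estimand that 7.3.1 and 7.1 do not describe, and no count of all referrals is defined as an outcome. The visit wording does not appear in the formula. A testable coefficient exists only in principle, because none is named and there may be two.

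**Conclusion.** The primary estimate has no valid denominator and should be corrected before outcome data are compared by arm. If both terms are the same referrals, the quotient says nothing about treatment: 1.0 per arm under the conditions in step 2, or about 143 per arm with a modelled total. If the denominator is all referrals, the quotient responds to treatment, but it is a share resting on a post-randomisation count. It is neither the referral rate of 7.3.1 nor the 5% and 10% rates powered in 7.1.

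The algebra for the first reading is exact for that ZIP specification. The percentages for the second rest on assumed volumes of other referrals. The finding concerns the stated estimate and the unnamed test; it does not show that a ZIP model is incapable of detecting an effect.

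**What to change.** Delete the division by average referrals and adopt one of the following.

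- **(a) Binary endpoint.** Analyse the proportion of eligible patients, fixed at randomisation, with at least one qualifying referral (mental health, sleep medicine or physical therapy) during the 9-month intervention. Use a binary model that allows for clustering by physician (a random effect, or GEE with robust standard errors), and report the risk difference or risk ratio. This is closest to the patient proportion in 7.1, although 7.1 does not itself specify at least one referral or the time window.
- **(b) Count endpoint.** Keep the count model, add log(eligible patients) or log(patient-months) as an offset, account for physician-level clustering, and name one marginal rate ratio as the primary test.

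With either option, state how the visit-worded cancer exclusion in 3.2 applies to the chosen denominator, and use the same definition in 7.1, 7.3.1 and 7.4.

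The cost is a small change to the analysis text and to the wording of the estimand. Option (a) does change the estimand from a count to a patient proportion, so it should be recorded as such. The eligible patients are already identified in the registry, and no new data are needed.
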